Appendix 9: SOP for lymph node puncture and Xpert MTB/RIF assay	43
Appendix 10: SOP for stools Xpert MTB/RIF assay.....	44
Appendix 11: SOP for urine Xpert MTB/RIF assay.....	47
Appendix 12: SOP for Xpert MTB/RIF assay performance	50
Appendix 13: SOP for the diagnosis of HIV in children	53
Appendix 14: Checklist for adherence counselling (HIV and TB)	55
Appendix 15: Anti-TB dosages for children ⁶	60
Appendix 16a: Weight for height in children from 5 to 10 year old	62
Appendix 16b: Weight for height in adolescents.....	63
Appendix 17: CRF Lab.....	64
Appendix 18: Interpretation of Trace results in Xpert MTB/RIF Ultra	70

1. Summary

Title	EVALUATING XPERT MTB/RIF ULTRA IN STOOLS AND URINE TO IMPROVE TB DIAGNOSIS IN CHILDREN
Design	Multicentric study (South Sudan and Guinea Bissau). Cross-sectional study.
Rationale	TB diagnosis in children is challenging in low-resource and conflict-affected settings, and a high number of children remain undiagnosed and untreated. A delay in TB diagnosis can lead to an increase in preventable morbidity and mortality. This study aims to provide more evidence of the utility of Xpert MTB/RIF Ultra in stools and urine for TB diagnosis in children, assuming a higher sensitivity than conventional microscopy and acknowledging that TB culture is rarely available in the contexts where MSF works.
Main objectives	To determine the sensitivity and specificity of Xpert MTB/RIF Ultra in stool and urine samples in suspected paediatric TB cases in comparison with the gold standard (Xpert MTB/RIF Ultra).
Secondary objectives	1. To determine the sensitivity and specificity of Xpert MTB/RIF Ultra rifampicin resistance using stools and urine in pulmonary and extra pulmonary TB confirmed and unconfirmed TB cases as composite. 2. To disaggregate according to HIV status (positive, negative) and to nutritional status (SAM or not). 3. Describe the prevalence of positive TB LAM in HIV-infected, HIV-uninfected and SAM patients with and without TB.
Population	Children with presumptive TB in Malakal (South Sudan) and in Bissau (Guinea Bissau).
Timeframe	January 2019 to July 2021.
Expected results	Show that stool and/or urine Xpert MTB/RIF Ultra can be a sensitive and specific tool for TB diagnosis in children. This evidence can lead MSF, WHO and National TB programs to recommend stool and urine Xpert MTB/RIF Ultra as routine tests for TB diagnosis in children.
Partnership	Ministry of Health in South Sudan Ministry of Health in Guinea Bissau

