In South Sudan, TB remains a major public health problem. According to 2016 WHO data, the estimated TB incidence (all forms of TB) in South Sudan was 146 per 100,000 population (11% affecting children) in 2016, with an overall treatment coverage of 54%. HIV prevalence in the

country and in Upper Nile region is 2.7%. Estimated rate of MDR TB in new and already treated cases is estimated to be 3 and 13% respectively (36). People living in IDP camps, have an increased risk to develop TB (37), and the estimated incidence in Malakal is 3.5 times higher than in the country, with high HIV co-infection (11%).

Médecins sans Frontières (MSF) started the intervention in Malakal (figure 1) by the end of 2013 due to a conflict crisis in the area which required big humanitarian needs. MSF is currently supporting primary and secondary health care in Malakal Protection of Civilians (POC) and Town, and supporting the rural area through a decentralised model of care. MSF is currently working without MoH staff at the facilities. HIV/TB support started in 2015 and is currently supporting a cohort of around 100 HIV patients and is currently providing TB-DRTB integrated care. All components of the program (diagnostic, medical care, counselling and health promotion-community engagement) are supported by MSF, even if all data is reported to National TB Program according to MoH requirements.

Figure 1:

- b. In 2017, a total number of 236 patients were diagnosed of TB and started on treatment. Among them, 34 (14%) were children, 14 among them under 5 years old. In 2018, the MoH placed Xpert MTB/RIF machine in MSF supported laboratory in Malakal POC. Improved diagnostic skills and community strategy with active case finding have increased the TB diagnosis by 25%, with 28 cases in the first 8 months of the year. Bissau (Guinea Bissau)*

In Guinea Bissau, TB remains a major public health problem. According to 2017 WHO data (38), the estimated TB incidence (all forms of TB) in Guinea Bissau was 374 per 100.000 population (15% affecting children) in 2017, with an overall treatment coverage of 32%. HIV prevalence in the country is 3.4% according to UNAIDS (39) and HIV coinfection in TB patients is as high as 32%. Estimated rate of MDR TB in new and already treated cases is estimated to be 2.5 and 14% respectively. The treatment success for new and relapse TB cases is 76 and 43% respectively.

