According to National TB Program data, in 2018 2200 persons were started on TB treatment and 45% among them were ≤ 15 years old.

MSF OCBA launched the permanent mission in Guinea Bissau (figure 2) in 2016 as a strategic choice with the objective to test and develop innovative medical strategies in paediatric care to decrease childhood mortality and which will ultimately help to overcome operational challenges, by being capitalized and exported to more unstable settings. MSF supports several departments in the Simão Mendes National Hospital in collaboration with MoH: paediatric intensive care unit (PICU), neonatal intensive care (NICU), in-patient therapeutic feeding centre (ITFC) and few beds in the paediatric ward. MSF is currently diagnosing TB in children and referring them to MoH / National TB program to initiate and continue treatment.

Figure 2:

6. Objectives

a. Main objective

To determine the sensitivity and specificity of Xpert MTB/RIF Ultra in stool and urine samples in suspected paediatric TB cases in comparison with the WHO recommended test (Xpert MTB/RIF Ultra in sputum sample or validated extrapulmonary sample).

b. Secondary objective

- 1) To determine the sensitivity and specificity of Xpert MTB/RIF Ultra rifampicin resistance using stools and urine in pulmonary and extra pulmonary TB confirmed and unconfirmed TB cases as a composite.
- 2) To disaggregate according to HIV status (positive, negative) and to nutritional status (SAM or not).
- 3) Describe the prevalence of positive TB LAM in HIV-infected, HIV-uninfected and SAM patients with and without TB.

7. Patients and Methodology

a. Study design

We plan to conduct a multicentric study in 2 different centres: Malakal (South Sudan) and Bissau (Guinea Bissau). The methodology for the evaluation of Xpert MTB/RIF Ultra in stools and urine will be a cross-sectional study.

b. Study sites

This study will be conducted in South Sudan in two different sites, the Malakal POC and the Malakal town, and in Bissau in one site, the Simão Mendes National Hospital.

c. Partnership and study coordination

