- Persistent fever ($>38^{\circ}\text{C}$) beyond one week after exclusion from classical causes such as malaria or pneumonia
- Persistence or aggravation of fatigue
- Chest radiographs imaging suggestive of tuberculosis

4. Case with diagnosis of tuberculosis (40,41)

- **Confirmed TB:** patients with Xpert MTB/RIF Ultra positive (or TB culture positive when available) in a respiratory sample (pulmonary TB) or in other sample, such as CSF, lymph node or other tissue/liquid (extra pulmonary TB); TB LAM positive in HIV-infected patients.
- **Unconfirmed TB:** no microbiological confirmation but clinical diagnosis of TB and started on anti TB treatment (as established in Appendix 5).
- **Unlikely TB:** good response to other treatments (antibiotic, nutritional support, etc.) and no suggestive symptoms after 1 week of admission and until the 2 month follow-up.

8. Study procedures

a. Identification of participants

Eligible children will be identified upon admission to paediatric ward, ITFC, PICU/NICU (in Bissau) or as suggestive cases in OPD. The identification of suspected TB cases will be mainly based on clinical criteria. A diagnostic algorithm (Appendix 4) will be applied to all suspected cases. The populations of interest for this study are hospitalized children, severely malnourished (SAM) and HIV positive or exposed children.

b. Laboratory

1. Sample collection

All patients included in the study will have requested one stool and one urine sample. The team will follow a specific SOP for respiratory sample collection (naso-pharyngeal aspirate, gastric lavage or spontaneous sputum), stools, urine and lymph nodes (or other validated extra pulmonary samples) as described in the appendixes. In hospitalized children, all samples will be collected during hospitalisation and patients not capable of producing the required sample (stools/urine) during this period will be excluded from the study. For ambulatory patients, samples will be collected within 2 hours and, if child not capable of producing stools/urine, samples will be requested to be brought by parents or guardians the day after.

2. Laboratory procedures

Xpert MTB/RIF Ultra will be performed to respiratory or extra pulmonary validated samples, stools and urine for all patients at baseline, and for those with negative results and persistent symptoms, will be repeated after 1 to 2 weeks.

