Appendix 5: TB diagnostic algorithm

- a) axillary temperature > 38°C
- b) Enlarged lymph nodes, gibbous, > 2 weeks diarrhoea, meningitis
- c) Comprehensive assessment includes:
 - a. Clinical assessment
 - b. Growth assessment
 - c. Bacteriological test (sputum collection, naso-pharyngeal aspirate, gastric lavage, lymph node aspiration):
 - Xpert MTB/RIF testing (sputum, nasopharyngeal aspirate, gastric lavage, lymph node aspirate, CSF);
 - Xpert MTB/RIF in stools and urine;
 - TB culture and DST (only at baseline):
- For children:
 - < 5 years old: do nasopharyngeal aspirate (Appendix 5)
 - From 5 years old until child can expectorate: gastric lavage (Appendix 6)
 - For children who can expectorate: sputum
 - d. POCUS (only at baseline)
 - e. HIV testing if not yet performed (Appendix 16)
 - f. When relevant and available: X-ray (CXR, spine)
- d) Xpert MTB/RIF positive, CXR showing suggestive lesions (e.g. hilar lymphadenopathy, upper lobe infiltrates, and miliary picture), gibbous.
- e) Broad spectrum antibiotics:
 - **If no signs of severity:**
 - First line: amoxicillin PO for 7 days (NO fluoroquinolones)
 - If a second course of antibiotics is needed: azithromycin PO for 5 days
 - **If signs of severity:**
 - Parenteral antibiotics (ceftriaxone ± cloxacillin if *S.aureus* is suspected)
 - If a second course of antibiotic is needed: azithromycin PO for 5 days
 - In addition: **PCP treatment** should be given presumptively to all HIV-exposed or infected children < 1 year of age and any older child with severe immune suppression and not on CTX prophylaxis. For all other HIV-exposed or infected children, it should be considered if there is poor response to broad spectrum antibiotics after 48 h
- f) Clinical response to broad-spectrum antibiotic does not rule out TB. Continue follow up to see if symptoms re-occur

[figure not shown]

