Appendix 12: SOP for Xpert MTB/RIF assay performance

Xpert MTB/RIF assay is based on hemi-nested real time PCR for simultaneous detection of M. tuberculosis (MTB) and rifampicin (RIF) resistance. The target is the *rpoB* gene, critical for detection of mutations associated to rifampicin resistance. Xpert MTB/RIF automates all aspects of real time PCR analysis, with results available in 2 hours.

Sample processing

The test can be performed using fresh sputum samples or decontaminated samples prior culture inoculation.

Procedure with fresh sputum samples:

- Ask the patient to rinse the mouth twice before collecting the sample.
- Collect a minimum of 1.5 ml good quality sputum.
- Follow the procedures outlined below:

Procedure for Xpert MTB/RIF*

Step 1	Step 2	Step 3
 Add the reagent 2:1 (v/v) to the sample and shake 10-20 times. Incubate at room temperature for 15 min.; during incubation repeat once shaking for 10- 20 times.	 With a pipette transfer the diluted sample into a cartridge.	 Insert the cartridge in the machine and start the test.

* Source: National Health Laboratory Services, South Africa.

Procedure for sediment samples:

- Sediments can be prepared according to standard decontamination procedure (NALC-NaOH method) and re-suspend with phosphate buffer.
- Ensure 0.5 ml is available for the test; add 1.5 ml of reagent for 0.5 ml of re-suspended sediment.
- Follow the procedure described in the above figure.

Interpretation of the results:

Proper test performance is ensured by 2 internal controls:

- Sample processing control (SPC) ensures adequate processing and monitors presence of inhibition.
- Probe check control (PCC) verifies that the steps of the tests (rehydration, filling of the cartridge, etc.) take place correctly.

When the test is completed the display can show:

- “MTB detected” expressed by levels (the higher the level, the higher the amount of MTB detected in the sample) or “MTB not detected”;
- RIF results expressed as “detected”, “not detected” or “indeterminate” are available only if MTB is detected.

Other possible results:

- Invalid: MTB invalid and SPC failed due to one of several reasons, such as inhibition;
- Error: MTB no result, SPC no result, PCC failed; fail of system components;
- No result: e.g. tests stopped during processing.

Storage of samples and cartridges:

Samples:

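### Secondary objective 1, as worded, asks for rifampicin-resistance accuracy in unconfirmed TB, where no reference rifampicin result exists; it may merge two aims, and in confirmed cases about two resistant children are expected

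*Combined protocol and SAP*

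**What the plan says.** Section 6.b, item 1, sets as a secondary objective the "sensitivity and specificity of Xpert MTB/RIF Ultra rifampicin resistance using stools and urine in pulmonary and extra pulmonary TB confirmed and unconfirmed TB cases", taken as a composite. The Summary repeats it: "in pulmonary and extra pulmonary TB confirmed and unconfirmed TB cases as composite".

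Four other places decide whether this can be done:

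- Section 7.e.4 defines unconfirmed TB as "no microbiological confirmation but clinical diagnosis of TB and started on anti TB treatment".
- The same section lets a child be confirmed on "TB LAM positive in HIV-infected patients", without a positive Xpert or culture.
- Appendix 12 says that rifampicin results "are available only if MTB is detected". Appendices 10 and 11 likewise tie the display of resistance on stool and urine to an MTB-detected result.
- Appendix 5 lists "TB culture and DST (only at baseline" in the comprehensive assessment. Section 7.e.4 makes a child with a positive culture a confirmed case.

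The sample size section (7.d.4) covers TB detection only. The analysis section (10) does not mention rifampicin.

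**The concern.** A sensitivity or a specificity needs a reference result in each child counted. By the protocol's own definitions an unconfirmed child has no positive reference sample, hence no reference rifampicin call. A resistant or susceptible call on that child's stool can be neither right nor wrong. The same holds for a child confirmed by LAM alone.

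Among the remaining confirmed children, susceptible results will be fairly common but resistant ones very few. A reported resistance sensitivity would then rest on a handful of children or none. The plan also does not say whether a reference-resistant child whose stool is MTB-negative counts as a miss or leaves the denominator. With such small counts, that choice alone can move the estimate from 100% to 50%. The results are intended for WHO and national programmes (section 13), where such a figure could be read as evidence for or against stool or urine as a resistance test.

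**Working it through.** **Is there a reference result?** The groups in section 7.e.4, set against the rule in Appendix 12:

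- Confirmed by Xpert on a respiratory or validated extrapulmonary sample: MTB is detected, so a rifampicin call is possible.
- Confirmed by culture: DST is possible, but the child is confirmed, so this supplies nothing for the unconfirmed group.
- Confirmed by LAM alone: no rifampicin call.
- Unconfirmed: no rifampicin call.

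This step needs no arithmetic and no assumption.

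**The plan's own figure.** With 60% sensitivity and precision 0.12 (section 7.d.4): 1.96² × 0.60 × 0.40 / 0.12² = 64.02, so 64 confirmed. Then 64 / 0.20 = 320 suspected, and 320 / 0.98 = 326.5, so 327. The stated figures reproduce.

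**Resistant children expected among 64.** The only resistance rates in the documents are the MDR estimates in section 5. For South Sudan: "Estimated rate of MDR TB in new and already treated cases is estimated to be 3 and 13% respectively". For Guinea Bissau they are 2.5% and 14%. They are a proxy, neither specific to rifampicin nor stated to be paediatric. With the new-case rates:

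- 64 × 0.025 = 1.60 and 64 × 0.03 = 1.92.
- At 32 per project: 32 × 0.03 + 32 × 0.025 = 1.76.
- Chance of none: 0.97^64 = 0.142 to 0.975^64 = 0.198.

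**Of these, also stool-positive.** A paired call needs MTB detected in stool too.

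- At the planned 60%: 64 × 0.60 = 38.4 pairs, with 1.60 × 0.60 = 0.96 to 1.92 × 0.60 = 1.15 resistant. Chance of none in 38 pairs: 0.97^38 = 0.314 to 0.975^38 = 0.382.
- Over the 45–83% stool range cited in the background: 1.60 × 0.45 = 0.72 to 1.92 × 0.83 = 1.59 resistant.

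The plan assumes the same 60% for urine and gives no separate range for it.

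**Precision (Clopper–Pearson, 95%).** For k correct out of k, the lower limit is 0.025^(1/k).

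- 2/2: 0.025^(1/2) = 0.158, so 16–100%.
- 1/2 (one stool-negative child counted as a miss): 1–99%.

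**Previously treated children.** Only TB treatment in the last 3 months excludes a child (section 7.d.3), so some may have been treated before. Their share is not given.

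- Assumed shares of 10% and 30% raise the expected resistant count among 64 from 1.76 to 2.4 and 3.8.
- Extreme case, with the previously-treated rate for every child and 83% stool detection: 64 × 0.13 × 0.83 = 6.9 to 64 × 0.14 × 0.83 = 7.4. For 7/7 the lower limit is 0.025^(1/7) = 0.590, so 59–100%.

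**Susceptible side.** About 38 pairs less one resistant leaves 37. Full agreement, 37/37, gives 90.5–100%; 36/37 gives 85.8–99.9%. This is a best case, because it assumes a valid rifampicin call on both samples in every pair.

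**The case against.** The strongest reply is that objective 1 was never about resistance. Section 7.d.4 uses Xpert MTB/RR as the name of the assay when it plainly means TB detection, so the phrase in objective 1 may be that label spelled out. A composite of confirmed and unconfirmed TB is also a natural TB-detection reference, and section 10 plans no rifampicin analysis. If so, the small-number arithmetic is beside the point and the defect is ambiguous wording. This stands as a real possibility. The text does say rifampicin resistance, in two places, so neither reading can be ruled out and the sponsor has to settle it.

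A second reply is that secondary objectives need not be powered, and section 10 promises 95% confidence intervals for frequencies, so 2/2 would show its own imprecision. That is fair as far as it goes. An interval does not supply the missing reference in unconfirmed children, nor say how stool-negative resistant cases are counted.

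Third, DST might serve as the reference. It cannot do so for unconfirmed children, and the lab CRF as shown (Appendix 17) has no culture or DST entry.

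A reader might go further and infer that the study needs more children, or that the main accuracy estimates are undermined. The documents support neither. The 64 confirmed cases are sized for TB detection, nothing sets a precision target for resistance, and the main objective has its own reference in section 6.a.

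**Conclusion.** The concern holds in this form: as literally worded, objective 1 cannot be computed for unconfirmed children or for those confirmed by LAM alone. That part follows from the protocol's definitions and is firm. Which aim was intended is less certain.

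On the rifampicin reading, agreement on susceptible results is roughly estimable in confirmed children, but resistance sensitivity is not. About two reference-resistant children are expected, of whom about one would also be stool-positive. The size rests on the MDR rates as a proxy, on mostly new cases and on 60% stool detection. The extreme case of about seven paired resistant children changes the number but not the conclusion.

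The wording should be corrected before analysis. The problem is confined to this secondary objective.

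**What to change.** First settle which aim was meant, then state the two aims separately in the Summary and in section 6.b.

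- **Rifampicin.** Agreement of the rifampicin call between stool (and, separately, urine) and the respiratory or validated extrapulmonary reference sample, among children with MTB detected and a valid rifampicin call on both. Report the 2×2 counts with exact 95% CIs. Count separately the reference-resistant children who were stool- or urine-negative, and the pairs without a valid rifampicin call, including trace or indeterminate results. Appendix 18 is devoted to trace results; its content could not be read here, so the rule should be aligned with it. Make no resistance-sensitivity claim.
- **TB detection, if the composite was meant for that.** A separate secondary analysis of confirmed plus unconfirmed TB against unlikely TB, beside the unchanged main analysis. Note with it that stool results can influence the unconfirmed label: section 8.c passes a positive stool with negative sputum to the study coordinator for clinical management, and Appendix 5 includes stool and urine Xpert in the diagnostic assessment.

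The cost is a rewording in two places and one agreement table per specimen. The rifampicin result becomes descriptive. The sample size does not change.

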0.6	369	189	93	64
0.7	323	165	81	56

With a precision of 12%, total number of 64 patients will be required to have a diagnosis of confirmed TB. If we assume that positivity of Xpert MTB/RR in sputum or validated extra pulmonary sample will be 20% (rate non-sick/sick = 4), we will need a total of 320 suspected TB patients will be needed (160 per project) to achieve 64 patients with confirmed TB (32 per project). We assume that 2% of the children won't be capable of producing stools, therefore the final sample size will be 327.

e. Definitions

1. SAM (severe acute malnutrition) in children:

- Children < 5 years old: Z-score weight / height <-3 and / or MUAC <11.5 cm, and / or bilateral oedema.
- Children 5-15 years old: weight for height < 70% (see table in Appendix 16) or bilateral oedema

2. HIV infection:

All patients with suspected TB will be tested for HIV, after consent of the legal responsible and pre-test counselling. The algorithm test will be adjusted to the age of the child (see Appendix 12). All children < 18 months will need PCR DNA for HIV diagnosis. All children ≥ 18 months and > 6 weeks of breastfeeding cessation will follow same diagnostic algorithm as for adults, which requires 3 positive rapid tests.

3. Suspected case of tuberculosis (40,41):

Any child with at least one of the following signs, symptoms or features is considered a **suspected case of tuberculosis** (Appendix 4):

- Persistent cough for more than 2 weeks
- Unexplained fever for more than a week
- Suspected extra-pulmonary tuberculosis (TBEP), e.g.:
 - Angular deformation of the spine (gibbous)
 - Lymphadenopathy
 - Subacute meningitis
 - Abdomen distended with ascites

- > 2 weeks of diarrhoea
- Painless enlarged joints
- Pleural effusion
- Other

All **HIV positive** and **SAM children**, as well as all **TB contacts**, will systematically and actively be screened for TB.

Tuberculosis screening in children is done on admission and during hospitalization. If children are not identified as suspected TB cases at admission, a new assessment will be done after 1 week of admission. In addition to the above criteria, tuberculosis is suspected based on the following signs, symptoms and characteristics during hospitalization:

- Low weight gain despite correct nutritional treatment
- Persistent pneumonia after adequate and well-followed antibiotic therapy
- Persistence of cough

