Appendix 16a: Weight for height in children from 5 to 10 year old

RECONSTRUCTED FROM BMI charts: height between 120,5 and 140,0 cm									
Reconstruction based on WHO 2007 references									
Older children from 60 months to 10 years (110,0 - 140,0 cm)									
MALE		Weight-for-Height (Standing up)					FEMALE		
-3	-2	-1	Median	cm	Median	-1	-2	-3	
14.4	15.6	17.0	18.5	110	18.6	17.0	15.5	14.2	
14.5	15.8	17.1	18.7	110.5	18.8	17.1	15.7	14.4	
14.6	15.9	17.3	18.9	111	19.0	17.3	15.8	14.5	
14.8	16.0	17.5	19.1	111.5	19.2	17.5	16.0	14.7	
14.9	16.2	17.6	19.2	112	19.4	17.7	16.2	14.8	
15.0	16.3	17.8	19.4	112.5	19.6	17.9	16.3	15.0	
15.2	16.5	18.0	19.6	113	19.8	18.0	16.5	15.1	
15.3	16.6	18.1	19.8	113.5	20.0	18.2	16.7	15.3	
15.4	16.8	18.3	20.0	114	20.2	18.4	16.8	15.4	
15.6	16.9	18.5	20.2	114.5	20.5	18.6	17.0	15.6	
15.7	17.1	18.6	20.4	115	20.7	18.8	17.2	15.7	
15.8	17.2	18.8	20.6	115.5	20.9	19.0	17.3	15.9	
16.0	17.4	19.0	20.8	116	21.1	19.2	17.5	16.0	
16.1	17.5	19.2	21.0	116.5	21.3	19.4	17.7	16.2	
16.2	17.7	19.3	21.2	117	21.5	19.6	17.8	16.3	
16.4	17.9	19.5	21.4	117.5	21.7	19.8	18.0	16.5	
16.5	18.0	19.7	21.6	118	22.0	19.9	18.2	16.6	
16.7	18.2	19.9	21.8	118.5	22.2	20.1	18.4	16.8	
AGE	16.8	18.3	20.0	22.0	119	22.4	20.3	18.5	16.9
year:month	16.9	18.5	20.2	22.2	119.5	22.6	20.5	18.7	17.1
06:08	17.1	18.6	20.4	22.4	120	22.8	20.7	18.7	17.2
06:09	17.5	19.0	20.6	22.4	120.5	22.8	20.8	18.8	17.3
06:10	17.9	19.2	20.8	22.5	121	22.9	20.9	18.9	17.3
6:11 / 7:00	18.0	19.3	21.0	22.9	121.5	23.0	20.9	19.0	17.4
07:01	18.3	19.6	21.1	23.1	122	23.1	21.0	19.1	17.6
07:02	18.5	19.8	21.3	23.3	122.5	23.3	21.1	19.2	17.7
07:03	18.6	20.0	21.6	23.4	123	23.4	21.2	19.4	17.9
07:04	18.8	20.1	21.8	23.8	123.5	23.6	21.4	19.5	18.0
07:05	18.9	20.3	22.0	24.0	124	23.8	21.5	19.7	18.1
07:06	19.1	20.5	22.2	24.2	124.5	24.2	21.7	19.8	18.3
07:07	19.2	20.6	22.3	24.4	125	24.4	22.0	20.0	18.4
07:08	19.4	20.8	22.5	24.6	125.5	24.6	22.2	20.3	18.7
07:09	19.7	21.1	22.7	24.9	126	24.9	22.4	20.5	18.9
07:10	19.8	21.3	23.0	25.1	126.5	25.1	22.6	20.6	19.0
7:11 / 8:00	20.0	21.5	23.2	25.3	127	25.3	22.7	20.8	19.2
08:01	20.2	21.6	23.4	25.7	127.5	25.5	23.1	21.0	19.3
08:02	20.3	21.8	23.6	25.9	128	25.9	23.3	21.1	19.5
08:03	20.5	22.0	23.8	26.1	128.5	26.1	23.4	21.5	19.6
08:04	20.6	22.3	24.1	26.3	129	26.3	23.6	21.6	20.0
08:05	21.0	22.5	24.3	26.7	129.5	26.7	24.0	21.8	20.1
08:06	21.1	22.6	24.5	26.9	130	26.9	24.2	22.0	20.3
08:07	21.3	22.8	24.7	27.1	130.5	27.1	24.4	22.1	20.4
08:08	21.5	23.0	24.9	27.3	131	27.5	24.5	22.5	20.6

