08:09	21.6	23.2	25.2	27.7	131.5	27.7	24.9	22.7	20.9
8:10 / 8:11	21.8	23.5	25.4	27.9	132	28.1	25.1	22.8	21.1
09:00	22.1	23.7	25.6	28.1	132.5	28.3	25.3	23.0	21.2
09:01	22.3	23.9	25.8	28.5	133	28.5	25.6	23.3	21.4
09:02	22.5	24.1	26.2	28.7	133.5	28.9	25.8	23.5	21.6
09:03	22.6	24.2	26.4	28.9	134	29.1	26.0	23.7	21.9
9:04 / 9:05	22.8	24.6	26.6	29.3	134.5	29.5	26.4	23.9	22.1
09:06	23.1	24.8	27.0	29.5	135	29.7	26.6	24.2	22.2
09:07	23.3	25.0	27.2	29.9	135.5	29.9	26.8	24.4	22.4
09:08	23.5	25.2	27.4	30.1	136	30.3	27.2	24.6	22.8
09:09	23.7	25.5	27.6	30.4	136.5	30.6	27.4	25.0	22.9
09:10	23.8	25.7	28.0	30.8	137	31.0	27.6	25.2	23.1
9:11 / 10:00	24.2	25.9	28.2	31.0	137.5	31.2	28.0	25.3	23.3
10:01	24.4	26.3	28.6	31.4	138	31.6	28.2	25.5	23.6
10:02	24.6	26.5	28.8	31.7	138.5	31.8	28.4	25.9	23.8
10:03	24.7	26.7	29.0	32.1	139	32.3	28.8	26.1	24.0
10:04	25.1	26.9	29.2	32.3	139.5	32.5	29.0	26.3	24.1
10:05	25.3	27.2	29.6	32.5	140	32.9	29.4	26.7	24.5

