Appendix 16b: Weight for height in adolescents

Weight adaptations between 140,0 (BMI charts WHO 2007) to 145,0 cm (NCHS 198

Reconstruction based on NCHS-CDC-WHO 1982 references

Adolescents from 10 to approx 18 years (140,0 - 165,0 cm)

MALE		Weight-for-Height (Standing up)					FEMALE		
70%	80%	85%	Median	cm	Median	85%	80%	70%	
25.1	27.2	29.6	32.5	140	32.9	29.4	26.7	24.5	
25.2	27.4	29.7	33.0	140.5	33.2	29.6	26.8	24.7	
25.2	27.6	29.9	33.4	141	33.6	29.8	27.0	24.9	
25.3	28.0	30.0	33.8	141.5	33.8	30.2	27.4	25.0	
25.4	28.2	30.2	34.1	142	34.1	30.4	27.6	25.2	
25.4	28.4	30.3	34.7	142.5	34.8	30.7	27.8	25.6	
25.5	28.8	30.5	35.0	143	35.6	31.1	28.0	25.7	
25.6	29.0	30.6	35.3	143.5	36.0	31.3	28.4	25.8	
25.6	29.1	30.8	35.7	144	36.4	31.4	28.6	25.9	
25.7	29.2	30.9	36.1	144.5	36.9	31.5	29.1	26.0	
25.8	29.2	31.0	36.5	145	37.1	31.5	29.7	26.0	
25.8	29.5	31.3	36.8	145.5	37.4	31.8	29.9	26.2	
26.0	29.7	31.6	37.2	146	37.8	32.1	30.2	26.5	
26.3	30.0	31.9	37.6	146.5	38.1	32.4	30.5	26.7	
26.5	30.3	32.2	37.9	147	38.4	32.6	30.7	26.9	
26.8	30.6	32.5	38.3	147.5	38.8	33.0	31.0	27.2	
27.0	30.9	32.8	38.6	148	39.1	33.2	31.3	27.4	
27.3	31.2	33.1	39.0	148.5	39.5	33.6	31.6	27.7	
27.5	31.5	33.4	39.3	149	39.8	33.8	31.8	27.9	
27.8	31.7	33.7	39.7	149.5	40.1	34.1	32.1	28.1	
28.0	32.0	34.0	40.0	150	40.5	34.4	32.4	28.4	
28.3	32.3	34.3	40.4	150.5	40.8	34.7	32.6	28.6	
28.5	32.6	34.7	40.8	151	41.2	35.0	33.0	28.8	
28.8	32.9	34.9	41.1	151.5	41.5	35.3	33.2	29.1	
29.1	33.2	35.3	41.5	152	41.9	35.6	33.5	29.3	
29.3	33.5	35.6	41.9	152.5	42.3	36.0	33.8	29.6	
29.6	33.8	35.9	42.3	153	42.6	36.2	34.1	29.8	
29.8	34.1	36.2	42.6	153.5	43.0	36.6	34.4	30.1	
30.1	34.4	36.6	43.0	154	43.4	36.9	34.7	30.4	
30.4	34.7	36.9	43.4	154.5	43.8	37.2	35.0	30.7	
30.7	35.0	37.2	43.8	155	44.2	37.6	35.4	30.9	
30.9	35.4	37.6	44.2	155.5	44.6	37.9	35.7	31.2	
31.2	35.7	37.9	44.6	156	45.1	38.3	36.1	31.6	
31.5	36.0	38.3	45.0	156.5	45.5	38.7	36.4	31.9	
31.8	36.3	38.6	45.4	157	46.0	39.1	36.8	32.2	
32.1	36.7	38.9	45.8	157.5	46.5	39.5	37.2	32.6	
32.4	37.0	39.3	46.2	158	47.0	40.0	37.6	32.9	
32.7	37.3	39.6	46.6	158.5	47.6	40.5	38.1	33.3	
33.0	37.7	40.0	47.1	159	48.2	41.0	38.6	33.7	
33.3	38.0	40.4	47.5	159.5	48.9	41.6	39.1	34.2	
33.6	38.4	40.8	48.0	160	49.7	42.2	39.8	34.8	
33.9	38.7	41.1	48.4	160.5	50.5	42.9	40.4	35.4	
34.2	39.1	41.5	48.8	161	51.6	43.9	41.3	36.1	
34.5	39.4	41.9	49.3	161.5	52.8	44.9	42.2	37.0	
34.8	39.8	42.3	49.8	162	54.5	46.3	43.6	37.8	
35.1	40.2	42.7	50.2	162.5	56.1	47.7	44.9	38.3	
35.5	40.5	43.1	50.7	163	56.4	47.9	45.1	38.8	

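### The 70% weight-for-height cut-off for SAM at 5–15 years does not match the Appendix 16 tables it cites, so the SAM strata are not uniquely defined from 110 cm to about 145 cm

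*Combined protocol and SAP*

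**What the plan says.** Section 7.e.1 gives two SAM rules by age. Below 5 years it is a Z-score rule: "Children < 5 years old: Z-score weight / height <-3 and / or MUAC <11.5 cm, and / or bilateral oedema". From 5 to 15 years it is a percent-of-median rule that refers to a table: "Children 5-15 years old: weight for height < 70% (see table in Appendix 16) or bilateral oedema".

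Appendix 16 has two parts:

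- Appendix 16a is labelled "Older children from 60 months to 10 years (110,0 - 140,0 cm". For each sex its columns are -3, -2, -1 and Median.
- Appendix 16b is labelled "Adolescents from 10 to approx 18 years (140,0 - 165,0 cm". Its columns are 70%, 80%, 85% and Median. Its heading says that weights between 140 and 145 cm are adaptations between two reference sets.

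SAM status is used in three places. Secondary objective 2 is "To disaggregate according to HIV status (positive, negative) and to nutritional status (SAM or not". Secondary objective 3 describes TB LAM positivity in groups that include SAM patients. Section 7.e.3 has all SAM children actively screened for TB.

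The clinical form (Appendix 4) records sex, date of birth, weight, size and a tick box for nutritional status. It shows no field for oedema and none for the rule used to tick the box.

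**The concern.** The definition sends staff to a table for a 70% threshold. For most of the height range of primary-school children, the table does not print that threshold. What it prints as its lowest cut-off is a Z-score column, the same kind of cut-off that section 7.e.1 uses for children under 5. Between 140 and 145 cm a column is headed 70%, but the weights in it are not 70% of the median printed in the same row.

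Two people who classify the same child in good faith could therefore reach different strata. The form records only the tick, so the rule behind it cannot be recovered from the tick itself. At stake is the meaning of the SAM and non-SAM groups in secondary objectives 2 and 3, and consistency in who is actively screened.

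**Working it through.** **Inputs.** All weights come from Appendices 16a and 16b. All 61 rows of 16a were used for each sex. From 16b, 19 rows were used: every row from 140 to 146 cm, plus 150, 155, 160, 162, 162.5 and 165 cm.

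**Formulas.** Ratio = cut-off weight / printed median × 100. Gap = cut-off weight − 0.70 × printed median.

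**1. Where the 70% figure reproduces.** In 16b at 150 cm, boys are 28.0/40.0 = 70.0% and girls 28.4/40.5 = 70.1%. Most rows checked from 145.5 cm upward lie within about half a point of 70%. The lowest is girls at 162.5 cm, 38.3/56.1 = 68.3%.

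**2. Appendix 16a, -3 column.** Each row runs boys -3, -2, -1, Median, then height, then girls Median, -1, -2, -3.

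- Highest ratio: "17.9 19.2 20.8 22.5 121 22.9 20.9 18.9 17.3". Boys at 121 cm: 17.9/22.5 = 79.6%.
- Lowest ratio: "25.1 26.9 29.2 32.3 139.5 32.5 29.0 26.3 24.1". Girls at 139.5 cm: 24.1/32.5 = 74.2%.

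| | Ratio, lowest | Ratio, highest | Gap, smallest | Gap, largest |
|---|---|---|---|---|
| Boys | 16.9/22.2 = 76.1% (119.5 cm) | 79.6% (121 cm) | 16.9 − 15.54 = 1.36 kg (119.5 cm) | 25.3 − 22.75 = 2.55 kg (140 cm) |
| Girls | 74.2% (139.5 cm) | 14.4/18.8 = 76.6% (110.5 cm) | 14.2 − 13.02 = 1.18 kg (110 cm) | 22.8 − 21.21 = 1.59 kg (136 cm) |

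The -2 column lies at 80.7–85.5% of median, so -3 is the printed column nearest to 70%.

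**3. One child.** For a boy of 130 cm, the -3 weight is 21.1 kg, and 70% of median is 0.70 × 26.9 = 18.8 kg. Without oedema, a boy of 20 kg is below the first and above the second.

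**4. Appendix 16b, column headed 70%.**

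| Height | Boys | Girls |
|---|---|---|
| 140 cm | 25.1/32.5 = 77.2% | 24.5/32.9 = 74.5% |
| 142 cm | 25.4/34.1 = 74.5% | 25.2/34.1 = 73.9% |
| 144 cm | 25.6/35.7 = 71.7% | 25.9/36.4 = 71.2% |
| 145 cm | 25.8/36.5 = 70.7% | 26.0/37.1 = 70.1% |

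**5. The shared row at 140 cm.** The girls' weights are identical in both tables (32.9, 29.4, 26.7, 24.5). In 16a they are headed Median, -1, -2, -3; in 16b, Median, 85%, 80%, 70%. The lowest weight therefore carries two labels. For a boy of 140 cm the documents allow three values: 25.3 kg (16a, -3), 25.1 kg (16b, 70% column) and 22.75 kg (0.70 × 32.5).

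**6. Coverage.** Appendix 16a starts at 110 cm, so a shorter child aged 5 or over has no row.

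**The case against.** The best reply is that the rule is stated once, in words, and can be applied. Appendix 16a prints a median for every height and sex, so 70% of it takes one multiplication. No text tells staff to use the -3 column at 5–15 years, and no column in 16a is labelled SAM. In 16b, staff who follow the instruction to read the table all get the same weight, and the heading discloses the 140–145 cm splice.

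Much of this stands. A reader might infer that staff will use the -3 column, or that the two sites will differ. The documents support neither as a fact; both are possibilities that the wording leaves open. The disclosed splice explains why the 16b ratios drift, but it does not make those weights 70% of median.

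A reader might also infer a biased comparison of accuracy between SAM and non-SAM children. The plan only disaggregates and describes. No test between the strata is planned, and nothing suggests that misclassification would depend on the stool or urine result. The strata will be imprecise in any case. If 20–50% of the planned 64 confirmed cases were SAM (an assumption; the documents give no figure), the stratum would hold about 13–32 cases. At the planned 60% sensitivity the 95% half-width is 1.96 × √(0.24/13) = 27 points to 1.96 × √(0.24/32) = 17 points.

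Finally, weight, size and sex are collected, so the anthropometric part can be rebuilt at analysis. That is true, but only after one rule is chosen, and oedema cannot be rebuilt from the form.

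**Conclusion.** The point holds as a conflict between a definition and the tables it cites. From 110 to 140 cm the threshold is not printed, and the lowest printed cut-off is 74.2–79.6% of median, 1.2–2.6 kg above 70%. From 140 to about 145 cm the column headed 70% starts at 77.2% (boys) and 74.5% (girls) and falls towards 70%. Children without oedema whose weight lies between the table value and 70% of median have no unique SAM status. Children classed by oedema are unaffected.

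The reach is limited to the descriptive SAM strata in secondary objectives 2 and 3 and to who is actively screened as SAM. The primary sensitivity and specificity of stool and urine testing do not use SAM status. The documents give neither the number of children aged 5–15 nor the number in the weight band, so no count of reclassified children and no effect on any accuracy estimate can be stated. The ratios rest only on the printed tables; the effect on classification rests on how staff read them, which the documents leave open.

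**What to change.** 1. Reconcile section 7.e.1 with Appendices 16a and 16b so that one rule, read one way, applies at every height, including children aged 5 or over who are shorter than 110 cm. This review takes no position on which cut-off is right.
2. Add a bilateral-oedema field to the clinical form, because the rule uses oedema and the form does not record it.
3. Derive the 5–15 year SAM stratum in the database from recorded weight, height, sex and oedema by that rule, and do not rely on the ticked box.
4. Optionally, show the strata under the alternative cut-off as well.

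The cost is a text correction, one form field and one derived variable. The downside is that oedema may be unrecoverable for children already enrolled; if so, the report should say how many were classed on weight and height alone. Recording of MUAC for the under-5 rule is a separate matter.
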